2. OBJECTIVES AND ENDPOINTS

2.1 Objectives

2.1.1 Primary Objective

The primary objective is to:

Compare absolute changes in selected biomarkers^a from Baseline^b to Week 24 (EOS) between adult smokers who continue to smoke conventional cigarettes (Control group) ad libitum and adult smokers who have completely^c switched to ad libitum use of test e-vapor products (Test groups) for 24 weeks.

^a Selected biomarkers include:

- o White Blood Cell Count (WBC Count)
- o High Density Lipoprotein Cholesterol (HDL-C)
- o Urinary 8-epi-prostaglandin F_{2α}
- o Urinary 11-Dehydrothromboxane B₂
- o Blood Soluble Intercellular Adhesion Molecule-1 (sICAM-1)
- o Urinary 4-(methylnitrosamino)-1-(3-pyridyl)-1-butanol and its glucuronides (total NNAL)
- o Carboxyhemoglobin (COHb)

^b Baseline of the 12-week ALCS-RA-16-06-EV study (CA20130), Week 1, will be used.

^c Subjects who exclusively use e-vapor products and have exhaled carbon monoxide (eCO) measurements ≤ 8 ppm from Week 6 (of the 12-week ALCS-RA-16-06-EV study) through Week 24 (EOS) and urine N-nitrosonornicotine (NNN) levels from

Week 6 (of the 12-week ALCS-RA-16-06-EV study) through Week 24 (EOS) consistent with switching to an e-vapor product.

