3. STUDY DESIGN

This research study is an extension of the 12-week ALCS-RA-16-06-EV study (CA20130). A total of up to 250 subjects (up to 100 in each of the Test groups and 50 in the Control group) who were compliant with the requirements of the 12 week ALCS-RA-16-06-EV study and continued to satisfy all inclusion/exclusion criteria of that study were planned to be enrolled. The sample size of the extension study is much smaller and the statistical analysis is mostly exploratory in nature.

The study utilized a parallel-group, open-label, controlled design and was conducted at multiple study sites. A total of 150 adult male and female (neither gender should account for more than 60% of the population) smokers (30 to 65 years of age, inclusive, determined at Screening [Visit 1] of the 12-week ALCS-RA-16-06-EV study) who completed the 12-week ALCS-RA-16-06-EV study (CA20130), were compliant with the requirements of the 12-week study, and continued to satisfy all inclusion/exclusion criteria of that study, were invited to enroll into this study and remain in the group into which they were randomized in the 12-week ALCS-RA-16-06-EV study.

- Control Group (n=52): Continue smoking under ad libitum use of subjects' own brand of conventional lit-end cigarettes, without use of any other type of tobacco/nicotine containing product, for the entire additional 12 weeks.

- Test 1 Group (n=50): Continue ad libitum use of test e-vapor products (Product XLCB), without use of any other type of tobacco/nicotine containing product, for the entire additional 12 weeks.
- Test 2 Group (n=48): Continue ad libitum use of test e-vapor products (Product XLMB), without use of any other type of tobacco/nicotine containing product, for the entire additional 12 weeks.

Subjects in the Test groups will be provided a 3-week supply of the test product to which they were randomized in the 12-week ALCS-RA-16-06-EV study and will be given a return date for Visit 2 (Week 15).

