4. ANALYSIS POPULATIONS

The Clinical Safety Population (CSP):

The CSP will consist of all subjects who are enrolled into this study and record at least one use of study products (i.e., conventional cigarettes or test e-vapor products) after Week 12.

The Modified Intent-to-Treat (mITT) Population:

The mITT population includes those subjects in the CSP population for which there is a baseline for a primary biomarker and at least one post-baseline biomarker measure for the primary biomarker after Week 12.

The Per-Protocol (PP) Population:

The PP population will be a subset of the mITT Population, which is comprised of subjects who completed the study without any major protocol violations, which are defined as:

- Control group: subjects who quit cigarette smoking (either by self report or NNN criteria of $\geq 80\%$ reduction in NNN from baseline at Visit 3 or 5).
- Test groups: subjects who self-report use of $> 10\%$ of baseline CPD over the course of the study*, subjects with an eCO > 8 ppm at any one visit in Visits 2 - 5, or subjects whose NNN levels are consistent with smoking cigarettes (ie, $< 80\%$ reduction in NNN from baseline) at Visit 3 or 5, and subjects who used ≤ 2 cartridges per week during any given week from Weeks 13 to 24.

*Baseline is defined as the CPD reported at Screening (Visit 2) of the 12-week ALCS-RA-16-06-EV study (CA20130), and the course of the study (post baseline) is defined as the average number of cigarettes smoked from Day 1, Week 1 of ALCS-RA-16-06-EV through the end of Week 24.

The CSP and PP populations will be used for the analyses of subject demographics, baseline characteristics and tobacco product use.

The mITT and PP populations will be used for the analyses of the primary endpoint. All other endpoints (excluding demographics, baseline characteristics, and safety data) will be analyzed based on the mITT population concept defined for each endpoint that includes subjects who has a baseline value and at least one post-baseline value. A PP population will be applied to the spirometry dataset using the criteria listed above.

The CSP will be used for the analyses of AEs, vital signs, clinical laboratory findings and other study safety related variables.

If it is determined that a subject was pregnant during the study, all of the pregnant subject's safety and biomarker data will be reported, but will be excluded from the biomarker summarization and statistical analyses.

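### The per-protocol cigarette limit for the Test groups is averaged over Weeks 1-24, which matches neither the Week 6 start in the primary objective nor the extension-only window of the other per-protocol criteria

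*SAP*

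**What the plan says.** Section 4 defines the PP set as mITT subjects who completed the study without a major violation. For the Test groups the first violation is "subjects who self-report use of $> 10\%$ of baseline CPD over the course of the study". A note to that bullet takes baseline as the CPD reported at Screening Visit 2 of the parent study. It says that the course of the study is "defined as the average number of cigarettes smoked from Day 1, Week 1 of ALCS-RA-16-06-EV through the end of Week 24".

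The same bullet lists three further violations, each sufficient on its own and each confined to the extension:
- "subjects with an eCO > 8 ppm at any one visit in Visits 2 - 5" (Weeks 15 to 24);
- "subjects whose NNN levels are consistent with smoking cigarettes", meaning a reduction from baseline of less than 80%, at Visit 3 or 5 (Weeks 18 and 24);
- two or fewer cartridges in any week from Week 13 to Week 24.

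Footnote c in Section 2.1.1 describes complete switchers as "Subjects who exclusively use e-vapor products and have exhaled carbon monoxide (eCO) measurements ≤ 8 ppm from Week 6" through Week 24, with NNN judged over the same period. Section 3 requires Test subjects to use the test product without other tobacco "for the entire additional 12 weeks". Under Section 6.3.1 the primary analysis is run on both the mITT and the PP sets.

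**The concern.** A PP set should hold the subjects who did what the objective describes. Here that means Test subjects who had switched completely, judged over the period that the objective and the extension define. A single mean over 24 weeks lets smoke-free weeks in the parent study offset cigarettes smoked in the extension. It also charges a subject for smoking in Weeks 1-5, before the Week 6 start in footnote c. The daily text-message report is the only measure that covers the days between visits, and the long average dilutes it. At stake is whether the PP estimate at Week 24 describes complete switchers.

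**Working it through.** The 10% limit is set by the plan and not derived, so there is no figure to reproduce. What can be checked is what the rule lets through.

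**Inputs.** Limit: more than 10% of baseline CPD, so exactly 10% passes (Section 4). Window: Weeks 1-24 (Section 4). Extension: Weeks 13-24 (Sections 3 and 4). Switching start: Week 6 (Section 2.1.1).

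**Formula.** Mean share of baseline = sum of (weeks × share of baseline smoked) / weeks in the window.

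**Smoking in the extension.**
- 0% in Weeks 1-12 and 20% in Weeks 13-24: (12 × 0 + 12 × 20%)/24 = 10.0%. Passes.
- 1% in Weeks 1-12 and 20% in Weeks 13-24: (12 × 1% + 12 × 20%)/24 = 10.5%. Excluded.
- 0% in Weeks 1-12 and 21% in Weeks 13-24: 12 × 21%/24 = 10.5%. Excluded.

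So 20% is the most that a constant extension rate can reach, and only after a smoke-free parent study.

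**Smoking before Week 6.** With share f in Weeks 1-5 and nothing afterwards, the mean is 5f/24. It exceeds 10% when f > 10% × 24/5 = 48%.
- f = 100% gives 20.8%, and f = 50% gives 10.4%. Both are excluded.
- f = 48% gives 10.0%, and f = 40% gives 8.3%. Both are kept.
- If Week 6 itself is counted as smoked, the cut-off falls to 10% × 24/6 = 40%.

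**Total allowance.** 10% × 24 = 2.4 weeks, or 16.8 days, at the full baseline rate.

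**The same two subjects under other windows.**

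| Window | None in Weeks 1-12, 20% in Weeks 13-24 | None from Week 6 |
|---|---|---|
| Weeks 1-24 (19 weeks from Week 6 at zero) | 10.0%, passes | 5f/24, excluded if f > 48% |
| Weeks 6-24 (19 weeks) | 12 × 20%/19 = 12.6%, excluded | 0%, passes |
| Weeks 12-24 (13 weeks) | 12 × 20%/13 = 18.5%, excluded | 0%, passes |
| Weeks 13-24 (12 weeks) | 20.0%, excluded | 0%, passes |

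The window therefore decides both cases. It is also labelled inconsistently. Sections 4 and 6.2.5 use Weeks 1-24, while the footnote in the shell of Table 14.2.2.1.3 defines its Weeks 1-24 column as the average over Weeks 12-24.

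**The NNN backstop.** If NNN fell in proportion to cigarettes (an assumption; the SAP does not say so), 20% of baseline would give an 80% reduction. The rule excludes reductions below 80%, so this subject sits exactly on the limit. With variation symmetric about that limit (also an assumption), the chance of failing at one or both NNN visits is 50% if the two errors are fully correlated and 1 − 0.5² = 75% if they are independent.

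**The case against.** The strongest reply is that the cigarette rule is one of four. A reader might infer that someone smoking 20% of baseline through the extension stays in the PP set, and the SAP does not support that. The subject needs a smoke-free parent study and must also pass eCO at four visits, NNN at two, and the weekly cartridge rule. Someone who smokes throughout is a recent smoker at every eCO visit. On the assumptions above, NNN alone would exclude this subject at least half the time. This stands, and it limits the claim to the self-report criterion.

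Second, the primary objective speaks of switching for 24 weeks, and in footnote c the Week 6 date is attached to eCO and NNN, with no CPD window stated. A Weeks 1-24 average is therefore not baseless. What remains is that the footnote qualifies what complete switching means, that the other PP criteria do not reach back to Week 1, and that a mean lets one period offset another.

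Third, entry required compliance with the parent study, so subjects who smoked heavily in Weeks 1-5 may be rare or absent. The SAP does not state that study's smoking requirement, so this can be neither confirmed nor dismissed. The biomarker criteria do not help here: they can only exclude further subjects and cannot restore one removed on self-report.

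Finally, PP is reported beside mITT, and Section 3 calls the analysis mostly exploratory. That is fair, and it lowers the severity.

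**Conclusion.** The mismatch is real and holds in conditional form. On the self-report criterion alone, smoking at up to 20% of baseline through the extension passes if no cigarettes were reported in Weeks 1-12. A subject with no cigarettes from Week 6 is removed if Weeks 1-5 averaged more than 48% of baseline. Neither result needs an assumption beyond steady rates within each period. How many subjects are affected cannot be derived from the SAP. With 50 and 48 subjects enrolled in the Test groups, each subject is about 2% of an arm (1/50 = 2.0%, 1/48 = 2.1%), and more of a smaller PP set.

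A reader might also infer that both errors bias the Test-Control difference toward zero. Only the first has that direction: retained smokers would dilute the difference, by an amount that cannot be stated without knowing their number. Dropping genuine switchers mainly reduces sample size, and no direction follows from it. The mITT result does not change. Severity is minor to moderate.

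**What to change.** In Section 4, keep the limit of more than 10% of baseline CPD but apply it to two means: Weeks 13-24 and Weeks 6-24. Exclude a Test subject who exceeds it in either. Both are needed. Weeks 13-24 alone would ignore smoking in Weeks 6-12, and Weeks 6-24 alone would still allow 10% × 19/12 = 15.8% of baseline throughout the extension after none in Weeks 6-12. Together they exclude the 20% extension smoker and keep the Week 6 switcher. Also correct the footnote in the shell of Table 14.2.2.1.3 so that its Weeks 1-24 average means Weeks 1-24, as in Sections 4 and 6.2.5.

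The cost is SAP wording and a re-derivation from daily reports already collected. A few subjects may move in or out of the PP set. Some tolerance remains: a 10% mean over Weeks 13-24 still permits 10% × 12 = 1.2 weeks at the full baseline rate, half of the present 2.4 weeks, so the eCO and NNN criteria should stay as they are.

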5. STUDY GROUP AND PRODUCT DESCRIPTIONS

The following products will be tested in this study:

- Product A = Test EVP (currently marketed by Nu Mark LLC as MarkTen® XL Bold Classic [4.0% NBW]) [CVR2.6.8] Formula: 10381-44-B; Name: "Rosetta"; Label: B44 (Product XLCB)
- Product B = Test EVP (currently marketed by Nu Mark LLC as MarkTen® XL Bold Menthol [4.0% NBW]) [CVR2.6.8] Formula: 10381-40-E; Name: "Spencer"; Label: 40E (Product XLMB)

The following groups will be tested in this study:

Test 1 Group: Exclusive ad libitum use of test e-Vapor Product XLCB, without use of any other type of tobacco/nicotine containing product, for the entire additional 12 weeks

Test 2 Group: Exclusive ad libitum use of test e-Vapor Product XLMB, without use of any other type of tobacco/nicotine containing product, for the entire additional 12 weeks

Test 1 + Test 2 Group = Combined e-vapor use group

Control Group : Continue smoking under ad libitum use of subjects' own brand of conventional lit-end cigarettes, without use of any other type of tobacco/nicotine containing product, for the entire additional 12 weeks

The following study group descriptions will be used in the footnotes for listings, tables, and figures.

Test 1 Group = e-Vapor Product XLCB

Test 2 Group = e-Vapor Product XLMB

Test 1 + Test 2 Group = Combined e-Vapor Use Group

Control Group = Continue smoking lit-end conventional cigarette

Study groups will be referred to in the text as: Test 1 Group, Test 2 Group, Combined Test Group, and Control Group.

6. BIOMARKER, PRODUCT USE, PULMONARY FUNCTION, AND QUESTIONNAIREASSESSMENT AND ANALYSIS

6.1 Biomarkers Sample Collection and Measurements

6.1.1 Urine Biomarkers of Exposure and Biomarkers of Potential Harm

6.1.1.1 Urine BOE and BOPH Sample Collection

The first urine void of the day will be collected by the subjects and brought to the study sites on Visit 3 and Visit 5. Aliquots will be taken for analysis of urine NE (nicotine, nicotine glucuronide, cotinine, cotinine glucuronide, trans-3'-hydroxycotinine, and trans-3'-hydroxycotinine glucuronide), total NNAL, NNN, 11-dehydrothromboxane B₂, and 8-epi-prostaglandin F_{2a}, and creatinine. The remaining volume will be used for bio-banking.

6.1.1.2 Bioanalytical Method

Urine aliquots for NE, total NNAL, NNN, 11-dehydrothromboxane B₂, and 8-epi-prostaglandin F_{2a} will be shipped to Celerion Bioanalytical Services for analysis. These samples will be analyzed using validated LC-MS/MS analytical methods.

Aliquots for creatinine will be shipped to the Celerion Clinical Laboratory for analysis.

Urine for bio-banking will be stored at Celerion until finalization of the CSR at which time they will be shipped to a long-term storage facility chosen by the Sponsor. The samples for future evaluation will be stored indefinitely and may be used to measure various biomarkers associated with tobacco use.

6.1.1.3 Urine Biomarker Analysis Variables

- Creatinine-adjusted NE, total NNAL, NNN, 11-dehydrothromboxane B₂, and 8-epi-prostaglandin F_{2a} concentration
- Creatinine-adjusted absolute urine biomarker change from Baseline*
- Creatinine-adjusted percent urine biomarker change from Baseline*

*Baseline values reported on Day 1 (Week 1) of the 12-week ALCS-RA-16-06-EV study (CA20130) will be used.

Creatinine-adjusted concentrations will be calculated as shown in Section [6.1.1.3.2](#). Absolute and percent change from baseline will be calculated as shown in Section [6.1.1.3.3](#).

6.1.1.3.1 Urine Nicotine Equivalents

Nicotine equivalents will be calculated as the molar sum of nicotine and 5 major nicotine metabolites. Values of individual components reported as below the limit of quantitation (BLQ) will be set to one-half of the limit of quantitation prior use in the calculation below. Missing urine data will not be imputed.

Nicotine equivalents ($\mu\text{g}/\text{mL}$) = (nicotine [ng/mL]/162.23 [mg/mmol] + nicotine-gluc (ng/mL)/338.36 [mg/mmol] + cotinine [ng/mL]/176.22 [mg/mmol] + cotinine-gluc [ng/mL]/352.34 [mg/mmol] + trans-3'-hydroxycotinine [ng/mL]/192.22 [mg/mmol] + trans-3'-hydroxycotinine-gluc [ng/mL]/368.34 [mg/mmol]) x 162.23 (mg/mmol) x 1 $\mu\text{g}/1000 \text{ ng}$

6.1.1.3.2 Urine Biomarkers Adjusted for Urine Creatinine

Urine creatinine concentration will also be measured in urine biomarker collection and will be used to adjust the concentration values of urine biomarkers as follows:

Nicotine Equivalents

Nicotine equivalents (mg/g creatinine) = $\frac{\text{nicotine equivalents } (\mu\text{g}/\text{mL}) \times 100}{\text{creatinine } (\text{mg}/\text{dL})}$

NNAL, total NNAL, NNN, 11-dehydrothromboxane B₂, and 8-epi-prostaglandin F_{2a}

Urine biomarker (ng/g creatinine) = $\frac{\text{urine biomarker } (\text{pg}/\text{mL}) \times 100}{\text{creatinine } (\text{mg}/\text{dL})}$

6.1.1.3.3 Urine Biomarker Change From Baseline

Urine biomarker change from Baseline will be calculated for creatinine-adjusted urinary NE, total NNAL, NNN, 11-dehydrothromboxane B₂, and 8-epi-prostaglandin F_{2a} as follows, where Baseline = values reported on Day 1 (Week 1) of the 12-week ALCS-RA-16-06-EV study (CA20130):

Absolute change from Baseline = Post Product Use Value – Baseline Value

Percent change from Baseline (%) = $\frac{(\text{Post Product Use Value} - \text{Baseline Value})}{\text{Baseline Value}} \times 100 \%$

6.1.2 Blood Biomarkers of Exposure and Biomarkers of Potential harm

6.1.2.1 Blood BOE and BOPH Sample Collection

Blood samples (approximately 4 mL each) will be collected via direct venipuncture for WBC count, sICAM-1 concentration, HDL-C concentration, and COHb saturation analysis at Visits 3 and 5.

6.1.2.2 Bioanalytical Method

Blood samples for WBC count, HDL-C concentration, and COHb saturation will be shipped to the Celerion Clinical Laboratory for analysis. Whole blood COHb saturation will be determined using a validated spectrophotometric method at the Celerion Clinical Laboratory, Lincoln, Nebraska.

Blood samples for sICAM-1 concentration will be shipped to Celerion Bioanalytical Services for analysis. These samples will be analyzed using validated LC-MS/MS analytical methods.

6.1.2.3 Blood Biomarker Analysis Variables

The following variables will be determined for blood biomarkers:

- Blood WBC count, sICAM-1 concentration, HDL-C concentration, and COHb saturation
- Absolute blood biomarker change from Baseline*
- Percent blood biomarker change from Baseline*

*Baseline values reported on Day 1 (Week 1) of the 12-week ALCS-RA-16-06-EV study (CA20130) will be used.

Absolute and percent change from baseline will be calculated as shown in Section [6.1.1.3.3](#).

6.1.3 Product Use and Compliance Data Collection and Analysis Variables

6.1.3.1 Data Collection

Product use (number conventional cigarettes used, number test e-vapor cartridges started, and number of puffs taken using the test products, either ≤ 20 or > 20) will be reported daily using a short message service. Exhaled CO (eCO) measurements will be performed by the clinic staff using the Micro+ basic™ Smokerlyzer® monitor (coVita) at Visits 3, 4, and 5. Use of other tobacco products will also be recorded at Visits 3, 4, and 5. Urine will be collected for determination of NNN at Visits 3 and 5.

6.1.3.2 Analysis Variables

- Average number of cigarettes per day by week
- Average number of e-vapor cartridges started per day by week
- Frequency and percentage of subjects with a reduction, no change, or increase in cigarettes used per day from Baseline (the cigarettes per day reported at Screening, Visit 2 of the 12-week ALCS-RA-16-06-EV study) to Visit 5 (Week 24)
- Frequency and percentage of subjects with a reduction, no change, or increase in e-vapor cartridges used per day from Baseline (the average e-vapor cartridges started per day during Week 1 of the 12-week ALCS-RA-16-06-EV study) to Visit 5 (Week 24)
- Measured eCO determined at Baseline, Visit 2, Visit 3, Visit 4, and Visit 5 (Week 24)
- Use of Other tobacco products (yes/no)
- Creatinine-adjusted urine NNN determined at Baseline*, Visit 3, and Visit 5 (Week 24) (calculated as described in Section [6.1.1.3.2](#))

*Baseline values reported on Day 1 (Week 1) of the 12-week ALCS-RA-16-06-EV study (CA20130) will be used.

6.1.4 Spirometry

6.1.4.1 Data Collection

Pulmonary function testing will be performed at Screening (Visit 2 of the 12-week ALCS-RA-16-06-EV study [CA20130]), Visit 3 (Week 18), and Visit 5 (Week 24).

6.1.4.2 Analysis Variables

The following pulmonary function parameters will be determined: measured FEV1, percent of predicted FEV1, measured FVC, percent of predicted FVC, measured FEV1/FVC, percent of predicted FEV1/FVC, FEV1 reversibility, percent FEV1 reversibility, and FEF25-75. Absolute change from baseline (Screening Visit 2 of the 12-week ALCS-RA-16-06-EV study [CA20130]) to Visit 3 and Visit 5 will be determined for all parameters.

6.1.5 Questionnaires

6.1.5.1 Data Collection

The QGEN, TQOLIT, and Cough questionnaires will be administered at Visits 3 and 5 and the mCEQ Questionnaire will be administered at Visit 5. The Reasons of Use/Not-Use Test Product Questionnaire will be administered for the test groups only at Visit 5.

6.1.5.2 Analysis Variables

- QGEN and TQOLIT questionnaires: responses, factor scores and the change in factor scores from Baseline* to Week 18 and Week 24
- Responses to each question on Cough Questionnaire at Baseline*, Visit 3 (Week 18) and Visit 5 (Week 24)
- Responses to Reasons for Use and Not-use of Test Product questionnaire at Visit 5 (Week 24) for test group only
- mCEQ: Response scores for each question, the factor scores for Smoking satisfaction, Psychological reward, Aversion, Enjoyment of sensation, and Craving reduction, and the change in factor scores from Baseline* to Week 24.

*Baseline values reported on Day 1 (Week 1) of the 12-week ALCS-RA-16-06-EV study (CA20130) will be used.

6.2 Data Summary and Presentation

The descriptive statistics tables for blood and urine biomarkers and products used per day will be generated with the following level of precision for the summary statistics:

The derived values (amount excreted in urine biomarkers, absolute change and percent change from Baseline) will have two decimal points. For blood biomarkers, the absolute change from baseline will have the same precision as the original values.

- n, n missing without a decimal;
- Mean/median with one more decimal/significant figure than minimum/maximum;
- Q1 and Q3 with one more decimal/significant figure than minimum/maximum;
- SD/SEM with one more decimal/significant figure than mean/median.
- CV% with one decimal;
- Minimum/maximum in same precision as in the database
- 95% CI with one more decimal/significant figure than minimum/maximum

